**VENTILATOR-INDUCED LUNG VORTEX IN
PATIENTS WITH SARS-CoV-2**

NCT04174313

MARCH 25, 2020

Materials and method

This study was conducted in the ICU dedicated to COVID-19 patients of an intensive care unit at a university hospital in Argentina. Approval was obtained from local institutional review board (resolution number: 68/2019) and informed consent followed the ethical committee's recommendations.

Inclusion criteria: This single-center prospective observational study evaluated consecutively admitted adult patients who were suffering from ARDS secondary to COVID-19 and needed volume-controlled ventilation (VCV) for at least 7 days. These eligibility criteria were decided in order to allow a minimum monitoring of the mechanical variables. Those who did not meet such requirement were excluded.

ARDS was defined according to the Berlin criteria (19) while the diagnosis of COVID-19 pneumonia was established based on CT images showing such condition and on real-time polymerase chain reaction (RT-PCR) test for coronavirus disease-2019.

Exclusion criteria: Patients with do-not-resuscitate (DNR) orders and pregnant women. Cardiac arrest before ICU admission. Extra corporeal membrane oxygenation (ECMO) requirement within the first 24 h of ICU admission and chronic obstructive pulmonary disease with gold class 3 or 4, or home oxygen therapy (20).

Procedure: Patients were administered sedatives and analgesics (propofol and fentanyl) to obtain a score of -5 on the RASS scale. The protective ventilatory strategy included: low tidal volume ventilation (6 ml/kg/PBW), plateau pressure limitation (Pplat: <30 cmH₂O) and prone positioning for severe hypoxemia (21). FiO₂ and PaCO₂ were adjusted to achieve SaO₂ between 92 and 96% and pH >7.20, respectively. PEEP was titrated according to the best compliance of the respiratory system (CRS), without exceeding the Pplat limit set. Neuromuscular blockers were administered to patients suffering from severe ARDS (PaO₂/FiO₂ <100) and to the ones with hypoxemia associated with asynchronies despite the administration of sedoanalgesia, Pplat >32 cmH₂O or that needed prone positioning to improve oxygenation.

Mechanical variables and PaO₂/FiO₂ were registered daily for 14 days or until initiating assisted ventilation. These data were obtained in passive mechanical conditions.

Ventilator-induced lung injury vortex was defined as a progressive increase in driving pressure (ΔP) as Vt remained constant or even decreased.

Refractory hypoxemia was defined as PaO₂/FiO₂ <100 despite the optimization of mechanical ventilation and prone positioning.

Respiratory mechanics: Peak airway pressure, plateau pressure, and total PEEP were measured. The value of driving pressure (ΔP : Pplat - PEEP total), static compliance of the respiratory system (CRS = Vt/ ΔP) and specific mechanical power (SMP: mechanical power/CRS) were calculated. Mechanical power was computed as: Peak airway pressure x Vt - (ΔP x Vt/2) x respiratory rate x 0.098 (13).

Complications: The following variables and complications were also observed during the period of analysis: incidence of pneumonia associated with mechanical ventilation (14), need for noradrenaline over 0.1 μ g/kg/min for more than 24 h, positive blood cultures, accumulated fluid balance, dialysis treatment, clinical and/or

echocardiographic evidence of heart failure, lactate ≥ 2 mmol/L in at least two consecutive samples, presence of persistent fever ($\geq 38^\circ$ at least once a day for three consecutive days), and the highest value of ferritin, D-dimer, C-reactive protein, troponin I and LDH obtained during the first 14 days of invasive mechanical ventilation.

Statistical analysis: Dichotomic data are reported as frequencies and percentages while continuous data are presented as mean (standard deviation) or median (interquartile range) as appropriate, depending on the normality of distribution. Kolmogorov–Smirnov test was used to test normality of distribution for continuous variables. Comparisons between the two groups (VILI vortex vs. No VILI vortex) and intragroup (day: 7 vs. day: 14) were analyzed by either an independent t-test or the Mann–Whitney test. Differences in categorical variables were assessed using the χ^2 or Fisher's exact test.

The mortality predictive model following refractory hypoxemia as well as mortality for any reason was analyzed on day 90 by means of ROC curves. Survival difference between both groups was analyzed through longrank test. Cox's proportional hazards regression test was used to study the relationship between VILI vortex intensity and accumulative risk of death from refractory hypoxia. The difference of driving pressure ($\Delta\Delta P$) between days 7 and 14 was regarded as VILI vortex intensity expression. That was the period in which we more frequently observed VILI vortex development.

Data analysis was conducted with MedCalc 11.4.3.0 statistical software (Mariakerke, Belgium) and a p-value of <0.05 was considered statistically significant.

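### Driving pressure is recorded for at most 14 days, so 'No VILI vortex' can only mean 'no vortex by day 14', and neither the group labels nor the log-rank comparison says so

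*Combined protocol and SAP*

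**What the plan says.** Four statements in Materials and method bear on this point.

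- **Entry** (Inclusion criteria): patients must have "needed volume-controlled ventilation (VCV) for at least 7 days". No maximum is given.
- **Recording** (Procedure): "Mechanical variables and PaO₂/FiO₂ were registered daily for 14 days or until initiating assisted ventilation". The next sentence adds: "These data were obtained in passive mechanical conditions". The plan does not say from which event the 14 days are counted.
- **Exposure** (Procedure): "Ventilator-induced lung injury vortex was defined as a progressive increase in driving pressure (ΔP) as Vt remained constant or even decreased". The definition has no onset window, no minimum rise and no minimum number of days.
- **Analysis** (Statistical analysis): "Comparisons between the two groups (VILI vortex vs. No VILI vortex) and intragroup (day: 7 vs. day: 14") are the comparisons named. Survival in the same two groups is compared by a log-rank test, and "mortality for any reason was analyzed on day 90 by means of ROC curves". Vortex intensity, the Cox covariate, is the change in driving pressure from day 7 to day 14. The reason given for that interval is: "That was the period in which we more frequently observed VILI vortex development".

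No late or undetermined class is provided, and no rule says how a vortex with late onset is classed.

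**The concern.** The exposure is observed over a short window, but the group name carries no time limit. A patient who is still sedated and passively ventilated on day 15 remains able to develop a vortex by the plan's own definition, yet no reading is taken that could show it. With only two groups, that patient stays in 'No VILI vortex', and a later death is counted there.

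Three results depend on the label: the between-group comparisons, the log-rank test and the reported frequency of vortex. Unseen late vortices would move the first two toward no difference and make the third too low. The timing statement has a related weakness. It can be compared with days 1 to 6, where readings exist, but not with any day after 14.

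**Working it through.** The documents give no sample size, event count, death rate or vortex frequency, so there is no stated figure to reproduce. The check has one part from the text and three illustrative parts. Every risk and rate below is an assumption.

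**1. Text.** Recording ends at day 14 or at assisted ventilation. Passive ventilation has no upper limit at entry. There are two exposure classes. Hence onset after day 14 in a passively ventilated patient gives 'No VILI vortex' by default. If the recording and mortality clocks start together (not stated), readings cover at most 14/90 = 16% of the horizon, leaving 90 − 14 = 76 days without them.

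**2. Dilution.** Let pV and pN be the true death risks with and without vortex, and m the share of the labelled no-vortex group with an unseen late vortex. Assume these patients die at the vortex-group rate. Then

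- observed no-vortex risk = pN + m(pV − pN)
- observed difference = (1 − m)(pV − pN)

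With pV = 60% and pN = 30%, and an illustrative 30 patients per group for power:

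| m | observed no-vortex risk | difference (points) | risk ratio | power |
|---|---|---|---|---|
| 0 | 30.0% | 30.0 | 2.00 | 65% |
| 5% | 31.5% | 28.5 | 1.90 | 61% |
| 10% | 33.0% | 27.0 | 1.82 | 56% |
| 20% | 36.0% | 24.0 | 1.67 | 46% |
| 30% | 39.0% | 21.0 | 1.54 | 37% |

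With 50% and 30%, the difference goes from 20 points to 19, 18, 16 and 14.

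**3. What m might be.** A simulation of 400,000 patients per scenario assumed:

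- vortex onset at 2% or 4% per day from day 2;
- exit from passive ventilation at 6% or 10% per day from day 8;
- a second or third successive daily rise needed before a vortex is called;
- true vortices counted to day 28.

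The share still passive on day 14 is then 0.94^7 = 65% or 0.90^7 = 48%, and on day 15 it is 0.94^8 = 61% or 0.90^8 = 43%.

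| Onset rate after day 14 | m | assumed 40-point difference becomes |
|---|---|---|
| unchanged | 5.7% to 17.9% | 40 × 0.943 = 37.7 to 40 × 0.821 = 32.8 |
| half | 3.4% to 11.7% | 38.6 to 35.3 |
| a quarter | about 2% to 8% | 39.2 to 36.8 |

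With the unchanged rate, 17% to 33% of all vortices to day 28 are missed.

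**4. Timing statement.** With a constant onset rate and no true clustering, 53% to 66% of detected vortices fall on days 7 to 14 if dated by the day of confirmation, but only about 38% to 50% if dated by onset. The result depends on the dating rule, which the plan does not give. Under either rule, nothing after day 14 is available for comparison.

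**The case against.** The strongest reply is that a fixed exposure window followed by a later outcome is an ordinary prognostic design. The plan uses day 14 consistently: for the peak biomarkers, the within-group comparison and vortex intensity. If the exposure is vortex by day 14, a patient without one by then is correctly classified. That stands, and for this reason the 14-day cap is not itself an error or a contradiction. But the design needs the groups labelled that way and survival handled to match, and the plan does neither.

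Several stronger readings are tempting, and the documents do not support them.

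- *A vortex starting on days 13 to 14 is certainly missed.* Because 'progressive' has no minimum number of readings or size, a short rise could be classed either way. The gap there is the definition, not the cap.
- *The Cox analysis is also affected.* Its intensity term uses days 7 and 14 only, and later readings would not change it.
- *The ROC analysis is contaminated.* The ROC sentence does not name vortex status as its predictor. Equally, day 90 is stated only there; no horizon is given for the log-rank test.
- *The window manufactures the clustering on days 7 to 14.* By onset day, under a flat rate, no more than about half of the detected vortices fall there. The sentence needs a qualifier, not deletion.

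It is also fair to say that a constant onset rate to day 28 runs against the investigators' impression of when vortex occurs, and that under a falling rate the dilution is modest. Moving the cap to day 28 would leave the same question for later days, and the text is in the past tense, so prospective extension may not be possible.

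**Conclusion.** The concern holds in a limited form. That a vortex starting after day 14 is labelled 'No VILI vortex' follows from the text without any assumed figure. So does the limit on the timing statement, which is valid only within the recorded 14 days.

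The size cannot be derived from the documents. The risk difference shrinks by (1 − m), and m is about 2% to 18% across the assumed onset rates. The effect is small if late vortex is rare and material if it is common. This rests on late-vortex patients dying at the vortex-group rate. On that basis the bias is toward no difference, so a reader should not infer that this flaw could create a false association between vortex and death. The plan should be changed because the change is cheap and alters both the log-rank comparison and what the study can conclude.

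**What to change.** 1. Define the exposure as 'vortex by day 14' and 'no vortex by day 14', and state the event from which the days are counted. Use these labels in every group comparison and conclusion.
2. In the survival comparison, either treat vortex as a time-dependent covariate that changes on the day of onset, or start survival at day 14 among patients alive then. Both use readings already taken.
3. Qualify the timing sentence so that it applies within the 14 recorded days.
4. Report how many patients were still passively ventilated at day 14, so that readers can bound m.
5. Where readings after day 14 are already charted for patients still passively ventilated, add them to the time-dependent series as a sensitivity analysis.

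The cost is a little more analysis work and a narrower conclusion. Starting survival at day 14 also drops earlier deaths from that comparison; the time-dependent version keeps them. No new measurement or procedure is needed.

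### The printed mechanical power formula applies respiratory rate and 0.098 to only one of its two terms; if it was followed, mechanical power and SMP are wrong by a factor that depends on rate and pressures

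*Combined protocol and SAP*

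**What the plan says.** The Respiratory mechanics paragraph gives the only specification of mechanical power: "Mechanical power was computed as: Peak airway pressure x Vt - (ΔP x Vt/2) x respiratory rate x 0.098". It cites a reference but gives no worked value and no second version of the formula. The same paragraph defines the related quantities:

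- driving pressure: "The value of driving pressure (ΔP : Pplat - PEEP total"), plateau pressure less total PEEP;
- compliance: "static compliance of the respiratory system (CRS = Vt/ ΔP");
- specific mechanical power: "specific mechanical power (SMP: mechanical power/CRS) were calculated".

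The units of Vt in the power formula and of CRS are not stated.

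The Statistical analysis paragraph plans "Comparisons between the two groups (VILI vortex vs. No VILI vortex) and intragroup (day: 7 vs. day: 14") without listing the variables compared. Vortex status does not involve mechanical power: "Ventilator-induced lung injury vortex was defined as a progressive increase in driving pressure (ΔP) as Vt remained constant or even decreased". Nor does the Cox covariate, since the difference in driving pressure "between days 7 and 14 was regarded as VILI vortex intensity expression".

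**The concern.** Read by the usual order of operations, the line is (Ppeak × Vt) − [(ΔP × Vt/2) × rate × 0.098]. The first term is energy per breath in cmH₂O·L. The second has been multiplied by breaths per minute and a unit conversion, so it is in J/min. The two cannot be subtracted; rate and 0.098 have to multiply both.

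A constant scale error would leave group comparisons intact. This error is not constant. It depends on respiratory rate and on the ratio of ΔP to peak pressure, so it differs between patients and between days. ΔP is also the quantity that separates the vortex from the no-vortex group, so the error can differ systematically between the groups being compared. If the printed form was used, comparisons of mechanical power between groups or between day 7 and day 14 could be shrunk or reversed, and comparisons of SMP could be shrunk.

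**Working it through.** **Inputs.** The formula, CRS = Vt/ΔP and SMP = power/CRS come from the Respiratory mechanics paragraph. The document gives no mechanical power value to reproduce, and no observed respiratory rates or pressures. All rates, pressures and volumes below are therefore assumptions: Ppeak 35 cmH₂O (range 30, 35, 40), ΔP 14 cmH₂O (range 10 to 20 in steps of 2), Vt 0.42 L, rates 12 to 30/min.

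**The two forms** (RR = respiratory rate)

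- Printed: Ppeak·Vt − 0.049·RR·ΔP·Vt
- Bracketed (correct): 0.098·RR·Vt·(Ppeak − ΔP/2)

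**Size of the error.** Vt cancels in the ratio:

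bracketed / printed = 0.098·RR·(Ppeak − ΔP/2) / (Ppeak − 0.049·RR·ΔP)

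This equals 1 at RR = 1/0.098 = 10.2/min. For example, at Ppeak 35, ΔP 14 and RR 20: (0.098 × 20 × 28) / (35 − 0.049 × 20 × 14) = 54.88 / 21.28 = 2.58. SMP carries the same ratio, because CRS is identical under both forms.

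| Rate (/min) | Fold too low, Ppeak 35, ΔP 14 | Range over the assumed grid |
|---|---|---|
| 12 | 1.23 | 1.21 to 1.29 |
| 15 | 1.67 | 1.58 to 1.92 |
| 20 | 2.58 | 2.27 to 3.77 |
| 25 | 3.84 | 3.09 to 8.91 |
| 30 | 5.71 | 4.07 upward |

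The open upper end at 30/min is one corner of the grid (Ppeak 30, ΔP 20), where printed power is close to zero.

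**Dependence on rate.** The derivative of the printed form in RR is −0.049·ΔP·Vt, which is negative for any positive ΔP. At Ppeak 35, ΔP 14 and Vt 0.42 L, going from 15 to 30/min takes bracketed power from 17.3 to 34.6 J/min, while the printed form goes from 10.4 to 6.1.

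**A rise in ΔP at constant Vt.** This pattern is compatible with the vortex definition. Let Ppeak go from 35 to 41 and ΔP from 14 to 20.

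- Bracketed power changes by (41 − 10)/(35 − 7) − 1 = 31/28 − 1 = +10.7% at every rate.
- Printed power changes by +9.2% at 12/min, +6.4% at 15, +0.6% at 20 and −9.6% at 26. When Ppeak and ΔP rise one-for-one, its derivative is Vt·(1 − 0.049·RR), which is negative above 1/0.049 = 20.4/min.
- At constant Vt, SMP is proportional to power × ΔP. Bracketed SMP changes by (31 × 20)/(28 × 14) − 1 = +58%. Printed SMP changes by +56% at 12/min, +44% at 20 and +29% at 26. It falls only above 33.0/min, the solution of 14·(35 − 0.686·RR) = 20·(41 − 0.98·RR).

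**A case where the sign is right.** If ΔP rises because PEEP is lower while Ppeak is unchanged, both forms change by −0.049·RR·Vt per cmH₂O, the same absolute amount.

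**The case against.** The strongest reply is that no calculation error has been shown. The evidence is one missing outer bracket in a prose formula that cites a source. Literal use would make power fall as rate rises and approach zero at some inputs, which the investigators might have noticed. A typographical slip is plausible, and loss of a bracket in reading the PDF cannot be fully excluded, although the inner brackets survived. This stands as a limit on the point: the document does not tell us what was computed. It does not remove the point, because the sentence is worded as a report of the calculation, is the only specification of the variable, and gives wrong values to anyone who follows it.

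It is also fair that the Statistical analysis paragraph never names mechanical power or SMP. Including them in the group and day comparisons is a reasonable reading, since they are derived continuous variables. Whether they enter the ROC analysis is unknown, because its predictors are not named.

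Reversal of direction needs particular conditions: a rate above 20.4/min with Ppeak and ΔP rising together for power, and a rate above 33.0/min for SMP in the step shown. At lower rates the SMP comparison is weakened, not reversed.

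Finally, the unstated CRS unit is only a labelling matter. If power uses litres, quoting CRS in mL or in L per cmH₂O changes SMP 1000-fold, but by a constant that alters no t-test, Mann–Whitney or ROC result. With a single Vt unit throughout, Vt cancels from SMP altogether. It carries no weight in the conclusion.

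**Conclusion.** The formula is wrong as written; operator precedence and dimensions are enough to show it, without the cited reference. Confidence in that is high. Any effect on results is conditional on the printed form having been used in the calculation file.

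If it was, mechanical power and SMP are understated at every rate above 10.2/min in the assumed ranges: about 1.6- to 1.9-fold at 15/min and 2.3- to 3.8-fold at 20/min, with larger errors at higher rates. These sizes rest on assumed pressures and rates.

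The damage is confined to mechanical power, SMP and any group, day 7 versus day 14 or ROC analysis that uses them. The vortex grouping, ΔΔP, the Cox model and the log-rank comparison rest on driving pressure and are untouched. This should be fixed, but it does not threaten the survival analyses.

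**What to change.** Replace the line with: mechanical power (J/min) = 0.098 × respiratory rate × Vt (L) × (peak airway pressure − ΔP/2). State the CRS unit used for SMP.

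Then check which form the calculation file used; one worked patient-day would settle it. If the file has the correct brackets, only the text changes. If it followed the printed form, recompute mechanical power and SMP from the recorded data and rerun the comparisons that use them.

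The cost is one corrected line, one added unit and one spreadsheet check. At worst, two derived variables are recalculated, with no new data collection.

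### The normality screen and the independent t-test are left unspecified, so skewed biomarkers can be summarised as normal and t-test error is not assured in unequal groups

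*Combined protocol and SAP*

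**What the plan says.** Under Statistical analysis, continuous data are summarised as mean (SD) or median (IQR) "as appropriate, depending on the normality of distribution". The next sentence names the screen: "Kolmogorov–Smirnov test was used to test normality of distribution for continuous variables". The one after it says that the comparisons "were analyzed by either an independent t-test or the Mann–Whitney test". The threshold is that "a p-value of <0.05 was considered statistically significant".

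The link from the screen to the choice of summary is explicit. The link from the screen to the choice of test is only implied, but no other selection rule is given.

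The variables most exposed are listed under Complications: "the highest value of ferritin, D-dimer, C-reactive protein, troponin I and LDH obtained during the first 14 days".

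The document does not state:
- whether KS uses standard or Lilliefors critical values, or whether it is run per group or on pooled data;
- whether the t-test is the pooled or the Welch version;
- any variance check or transformation;
- a target sample size or group sizes;
- the spread of any biomarker.

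**The concern.** There are two concerns, and they are separate faults.

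**The screen.** KS with the mean and SD estimated from the same data is very conservative unless Lilliefors critical values are used. In small groups it will often fail to reject normality. The five biomarkers are non-negative 14-day maxima, so right skew is a reasonable expectation. A skewed marker that passes is reported as mean (SD) and compared on the raw scale.

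**The t-test.** The groups are formed by observed vortex status, so neither their sizes nor their spreads are balanced by design. A pooled-variance t-test holds its 5% level under unequal spread only when the groups are about equal in size.

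At stake are the descriptive tables and the between-group p-values for continuous variables.

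**Working it through.** The document states no power, SD or group size, so there is no figure of its own to reproduce. From the document come alpha 0.05 (two-sided assumed), the KS screen, the t-test or Mann–Whitney pair, and two groups defined by vortex status. All sizes and distributions below are assumptions.

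**1. How often the screen passes skewed data.** Simulated lognormal samples, mean and SD estimated from the sample, 20,000 replicates per cell. Share passed as normal at 5%:

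| n | KS variant | log SD 0.5 | log SD 0.8 | log SD 1.0 |
|---|---|---|---|---|
| 20 | uncorrected | 98.5% | 90.7% | 80.5% |
| 40 | uncorrected | 92.8% | 61.3% | 35.9% |
| 100 | uncorrected | 58.3% | 4.8% | 0.3% |
| 20 | Lilliefors | 66.3% | 35.4% | 21.1% |
| 40 | Lilliefors | 40.4% | 8.0% | 2.0% |

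The uncorrected test rejects truly normal data in about 0.01% of samples instead of 5%, which explains its weakness.

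**2. What a wrong pass does to the summary.** Take a lognormal with log SD 1 and median 1. Its mean is exp(0.5) = 1.65 and its SD is √[(e − 1)e] = 2.16. Mean minus one SD is 1.65 − 2.16 = −0.51, for a quantity that cannot be negative.

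**3. What a wrong pass does to type I error.** With the same lognormal in both groups and unequal sizes, the t-test after a pass, and the screen-then-test rule overall, reject in 4.7% to 5.9%. Skewness alone does little.

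**4. What it does to power.** Lognormal, log SD 1, two-fold difference, 20 vs 35 patients. Applying screen-then-test gives 62–68%, Mann–Whitney throughout 65–66%, and a t-test on logs 67–69%. A loss of about 3–6 points appears only with uncorrected KS and the lower values in the smaller group.

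**5. Pooled t-test under unequal size and spread.** For normal data with equal means, let

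- s² = [(n₁−1)σ₁² + (n₂−1)σ₂²]/(n₁+n₂−2), the expected pooled variance;
- A = s²(1/n₁ + 1/n₂), the variance that the test assumes;
- B = σ₁²/n₁ + σ₂²/n₂, the true variance.

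The error is then approximately 2[1 − Φ(t_crit·√(A/B))], with t_crit = 2.00 on 58 df.

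| n₁:n₂ | σ₁:σ₂ | s² | A | B | √(A/B) | Formula | Simulated |
|---|---|---|---|---|---|---|---|
| 20:40 | 2:1 | 115/58 = 1.983 | 0.149 | 0.225 | 0.813 | 10.4% | 11.2% |
| 15:45 | 2:1 | 100/58 = 1.724 | 0.153 | 0.289 | 0.728 | 14.5% | 15.5% |
| 20:40 | 1:2 | 175/58 = 3.017 | 0.226 | 0.150 | 1.228 | 1.4% | 1.8% |
| 15:45 | 1:2 | 190/58 = 3.276 | 0.291 | 0.156 | 1.368 | 0.6% | 0.8% |

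Welch's test gives 4.9–5.2% in these cells. With an SD ratio of 1.5 (sizes 10:30, 12:48, 15:35, 20:40), the pooled error is 8.3–12.6% if the smaller group is more variable and 1.3–2.6% if the larger is. With equal sizes it stays at 4.7–5.8%.

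**6. Limits of the alternatives.**
- Raw-scale Welch after a KS pass, on lognormal data with equal means but unequal log SDs and unequal sizes, has error of 5.0% to 14.4%. Welch alone does not cure skewness.
- Mann–Whitney on normal data with equal means and a two-fold SD ratio rejects in 8.3% (20:40) to 9.3% (10:30) when the smaller group is more variable, and 3.2% to 1.9% when the larger is.
- On lognormal data with equal means and unequal log SDs, Mann–Whitney rejects in 8.6% to 39.1% of unequal-size comparisons, because it does not test means.

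**The case against.** The strongest reply is that the plan already provides a non-parametric route. A reader might infer a large loss of power from the raw t-test's 56% in the 20 vs 35 scenario, against 67% on logs. That figure applies the t-test to every sample, which the plan does not do: samples that fail the screen go to Mann–Whitney. Step 4 shows that the rule as a whole performs about as well as Mann–Whitney throughout. This objection stands.

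A reader might also infer that the biomarkers were in fact passed as normal. The document gives neither n nor the KS variant, and with Lilliefors or about 100 patients most samples with log SD 0.8 or more would be caught. Nor does it give any biomarker spread. The claim can only be that the screen may pass them.

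A third tempting reading is that the t-test rejects too often. That requires a pooled test and a smaller group that is also the more variable one, and the document states none of these. If the larger group is more variable, the test is conservative.

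Finally, the biomarkers are secondary observations, and the ROC, log-rank and Cox analyses do not pass through this screen. That lowers the stakes. It does not answer the point that the plan leaves both variants open when a rule free of these problems is available.

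**Conclusion.** The concern holds in conditional form. With small groups and uncorrected KS, skewed peak biomarkers can pass as normal. The harm is mainly a misleading mean (SD), with type I error near 5% when both groups share the same distribution and at most a few points of power lost. With a pooled t-test and groups unequal in both size and spread, error moves to about 11–15% or to about 1–2%, depending on which group has twice the SD (20:40 and 15:45), against about 5% for Welch.

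These magnitudes rest on assumed sizes, lognormal or normal shapes, and assumed SD ratios. The document neither confirms nor excludes them. The mortality analyses are unaffected, so this is a modest improvement to the analysis and not a threat to the main conclusions.

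**What to change.** In the Statistical analysis section:

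- Remove the normality pre-test as the basis for choosing summaries and tests.
- Use Welch's t-test for between-group comparisons of means.
- Prespecify log-scale analysis for ferritin, D-dimer, C-reactive protein, troponin I and LDH: Welch on logs, reported as a geometric mean ratio with 95% CI, with median (IQR) as the summary.
- If Mann–Whitney is kept, describe it as a test of distributional shift. It does not test means and is not protected against unequal spread.
- If the screen is retained for description, state the KS variant and whether it is applied per group.

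The same sentence also covers the within-group day 7 vs day 14 comparison. That comparison is paired and needs its own method, so Welch's test is not the remedy there.

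The cost is a change of wording and a re-run on data already held. Welch loses slight efficiency if the variances are truly equal. The log-scale estimand is a ratio of geometric means, which should be said when reporting.

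### Day-14 lung mechanics exist only for patients alive and still passively ventilated, yet day 7 is compared with day 14 by independent-sample tests, so selective exit can bias the result

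*Combined protocol and SAP*

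**What the plan says.** Four statements in Materials and method bear on this point.

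- **Inclusion criteria.** Patients must have "needed volume-controlled ventilation (VCV) for at least 7 days", and "Those who did not meet such requirement were excluded". No rule is given for a patient who leaves between day 7 and day 14.
- **Procedure, recording window.** Mechanical variables and PaO₂/FiO₂ were "registered daily for 14 days or until initiating assisted ventilation".
- **Procedure, measurement condition.** "These data were obtained in passive mechanical conditions".
- **Statistical analysis.** "Comparisons between the two groups (VILI vortex vs. No VILI vortex) and intragroup (day: 7 vs. day: 14" are the planned contrasts; for continuous variables they "were analyzed by either an independent t-test or the" Mann–Whitney test.

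The documents do not say which patients enter the day 7 versus day 14 comparison. They give no missing-data rule, repeated-measures model or sensitivity analysis, and no count of patients remaining on each day.

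**The concern.** Day 7 and day 14 are two readings on the same patients, but the stated tests treat them as two separate samples. This creates two problems.

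First, the within-patient correlation is ignored, so the standard error of the change is wrong.

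Second, an independent test accepts all day-7 patients on one side and only the day-14 remainder on the other. Leaving is plausibly related to lung state: improvement leads to assisted ventilation, and deterioration may lead to death. If so, the day-14 mean differs from the day-7 mean partly because the set of patients has changed. The day-14 difference between vortex and no-vortex groups is exposed in the same way.

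The study's subject is how mechanics evolve over days 7 to 14. A shift produced by who remains could be read as a change in the lungs.

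**Working it through.** The documents state no sample size, SD, effect size or exit rate, so there is no figure of the plan's to reproduce. Every numerical input below is an assumption, used only to show how the bias behaves.

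**1. Who has a reading.** Day 7: essentially everyone, by the entry rule. Day 14: only those alive and still passively ventilated, by the recording rule.

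**2. What each analysis estimates.** Let δ14 be the remainers' mean day-14 value minus the mean that all patients would have had on day 14, and let δ7 be the same shift in day-7 values.

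- All day-7 patients versus remaining day-14 patients: true change + δ14.
- Patients with both readings: true change + δ14 − δ7. With equal SDs, correlation r and exit depending on the day-14 value, δ7 = r·δ14, so the bias is (1 − r)·δ14. At r = 0.6 this is 0.4·δ14.

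Pairing therefore shrinks the bias but does not remove it.

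**3. Effect of ignoring the correlation.** With the same patients on both days, the true standard error is √(1 − r) = √0.4 = 0.63 of the one the independent test uses. The test then rejects only beyond 1.96/0.63 = 3.1 true standard errors. It is too conservative when nobody leaves selectively, and this partly masks the composition bias when they do.

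**4. Simulation, true change 0.** Assumed: driving pressure mean 13 and SD 3 cmH₂O on both days, r = 0.6, and log-odds of leaving falling by the stated slope per SD of day-14 driving pressure. Results for n = 100 with 40% leaving (1,500 replicates for rejection rates):

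| Exit slope | Apparent change, all day 7 vs remainers | Apparent change, both readings | Rejects: unpaired, all day 7 | Rejects: unpaired, both readings | Rejects: paired |
|---|---|---|---|---|---|
| 0 (unrelated) | −0.01 | −0.01 | 1% | 0% | 4% |
| 0.5 | +0.56 | +0.22 | 13% | 1% | 10% |
| 1 | +1.00 | +0.40 | 56% | 4% | 21% |
| 2 | +1.48 | +0.60 | 96% | 14% | 41% |
| −1 (high pressures leave) | −0.98 | −0.39 | 56% | 5% | 22% |

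The third column is 0.4 times the second, apart from the zero row, as step 2 predicts (for example 0.4 × 1.48 = 0.59). With 20% to 60% leaving and slopes 0.5 to 2, the apparent rise runs from +0.3 to +2.2 cmH₂O using all day-7 patients, and from +0.1 to +0.9 using those with both readings.

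**5. Day-14 group difference.** Assumed CRS: day-7 means 34 (vortex) and 36 (no vortex) mL/cmH₂O, slopes −1.0 and +0.5 per day, between-patient SD 8, slope SD 1.0, reading SD 2. The full-cohort difference at day 14 is (34 − 7.0) − (36 + 3.5) = −12.5. With exit to assisted ventilation rising with CRS and death likelier below about 18, remainers showed −8.9 to −9.9. With exit unrelated to CRS they showed −12.3, essentially unbiased.

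**6. Does a mixed model help?** For CRS in a no-vortex group with true change 0:

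| Exit follows | Unpaired | Paired | Mixed model, all daily readings |
|---|---|---|---|
| Recorded readings | −3.3 | −0.7 | 0.0 |
| Underlying trajectory | −3.6 | −1.1 | −0.3 |

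Another run with exit driven by the underlying trajectory left about −1.5 in the mixed model. The model does better than the unpaired test in each case but is not always unbiased.

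**The case against.** The strongest reply is that nothing here shows an actual bias. There are no counts, exit rates or reasons for leaving, and steps 4 and 5 show no bias when exit is unrelated to mechanics. That stands, and it limits the conclusion to what the plan permits.

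Three stronger readings are tempting, and the documents do not support them.

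- A reader might infer that both comparisons use only patients still passive on day 14. The plan does not say so, and the between-group comparisons are not confined to day 14. If only remainers were used on both days, the patient mix would be the same and the bias smaller.
- A reader might infer that the group gap is understated, or that no-vortex lungs would falsely appear to worsen. Either depends on who leaves, and the sign can reverse. The −12.5 benchmark also extends CRS to patients who have died or left passive ventilation.
- A reader might infer that days 8 to 13 are discarded altogether. Vortex is defined as a "progressive increase in driving pressure (ΔP) as Vt remained constant or even decreased", which plausibly uses the serial readings for grouping.

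Two further objections shape the remedy. Because groups are defined by the driving-pressure trajectory and CRS = Vt/ΔP, a group-by-day test on either variable is partly circular. For the same reason, the illustrative CRS model, which fixes group in advance and lets some vortex patients improve, does not mirror the plan's grouping. And the mixed model's 0.0 rests on exit following recorded readings, with variance components set to their true values in at least one of the runs giving that figure.

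Finally, the Cox covariate ΔΔP also needs a day-14 value. That is a related gap but a separate question, not argued here.

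**Conclusion.** The concern holds in limited form. It follows from the text that day-14 mechanics and PaO₂/FiO₂ come from a selected remainder, that day-7 values come from nearly everyone, and that the stated test for the within-group comparison is wrong for repeated readings on the same patients. That exit depends on lung state is plausible but assumed.

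If it does, the illustrated bias in driving pressure ranges from about 0.3 to 2.2 cmH₂O in either direction under the unpaired comparison using all day-7 patients, and is about 0.4 times that among patients with both readings. If it does not, the bias is nil, and the remaining fault is the lost precision of an unpaired test. Neither that selection drives the result nor that it runs in a given direction can be claimed from these documents. The change is worth making because it is cheap and uses data already registered.

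**What to change.** In the Statistical analysis section:

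1. Replace the independent day 7 versus day 14 tests of the mechanical variables and PaO₂/FiO₂ with a linear mixed model on all registered daily readings from day 7 to day 14. Fixed effects are group, day and group-by-day, with a random intercept and slope per patient and a log scale where a variable is skewed.
2. Report the within-group change and the fitted day-14 values with 95% confidence intervals, read as change while alive and passively ventilated.
3. Label group-by-day effects on driving pressure and CRS as descriptive, because the groups are defined by the driving-pressure trajectory.
4. Report, by group and day, the number still passively ventilated and the reason for leaving (assisted ventilation or death).
5. Add one sensitivity analysis for informative exit, for example a joint model of the readings and the time to leaving.

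The cost is SAP wording and modest extra analysis, with no new mechanical measurements. The small downside is that the mixed model assumes exit depends on the recorded readings; where it does not, the model only reduces the bias. Items 4 and 5 are there to show how much this matters.
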